9.4.3. Secondary Endpoint(s)/Estimand(s) Analysis

Statistical analysis for secondary endpoints will include descriptive statistics for the following pharmacokinetic parameters:

221030

Protocol Version No. 1.0

Albendazole: AUC0-∞, Tmax, t1/2, λz and AUC %Extrap obs

Albendazole sulfoxide: AUC0-∞, AUC0-t, Cmax, Tmax, t1/2, λz and

AUC %Extrap obs.

TMF-16298784

Descriptive statistics (N, n, arithmetic mean, 95% CI of arithmetic mean, SD, median, minimum, maximum and geometric mean with 95% CI) will be presented for untransformed secondary PK parameters.

Average values of Test Study Intervention-T and Reference Study Intervention-R for PK parameters for each participant will be calculated and reported. Descriptive statistics will be calculated and reported for the same data.

Individual values of PK parameters for Test Study Intervention-T (first administration), Test Study Intervention-T (second administration), Reference Study Intervention-R (first administration) and Reference Study Intervention-R (second administration) for each participant will be calculated and reported. Descriptive statistics will be calculated and reported for the same data.

In case of treatment discontinuation due to any reason, only the data available before the occurrence of intercurrent event will be used to estimate secondary PK parameters using while-on-treatment policy strategy.

If any participant experience emesis/vomiting or if a prohibited/rescue medication is used by any participant, the participant's data for that period will not be used for the analysis of secondary endpoints related to PK using hypothetical strategy.

Treatment policy strategy will be used to analyze the secondary endpoints related to safety to make use of all available data for a participant.

9.4.4. Safety Analysis

Safety data will be presented in tabular and/or listing format and summarized descriptively. Number and percentage will be presented for incidence of AE.

Descriptive statistics (N, n, mean, SD, median, minimum and maximum) will be presented for absolute and change from baseline values of vital signs parameters at each timepoint.

Comprehensive description for statistical analyses of safety endpoints will be described in the SAP.

9.5. Interim analyses

Not Applicable

9.6. Sample size determination

Based on the WHO guideline for albendazole, the maximum intra-subject variability observed for primary pharmacokinetic parameters Cmax and AUC(0-t) could be up to ~

TMF-16298784 Protocol Version No. 1.0

68% and 62% respectively. For this sample size calculation, a product difference of up to 10% (i.e. T/R ratio as 90.0-111.1%) has been assumed.

The sample size was determined using R software considering the following assumptions:

- a. T/R ratio = 90.0-111.1%
- b. Intra-Subject CV (%) $\sim 68\%$ (Cmax) and 62% (AUC(0-t)), or 48% (both)
- c. Significance Level = 5%

Correlation between Cmax and AUC(0-t) was calculated to be very high, based on an inhouse albendazole study (GSK study O7921353). The exact Cmax and AUC(0-t) covariance matrix was calculated from this historical study (Table 10) and used to simulate realistic Cmax and AUC(0-t) values based on multivariate normal distributions. These values were then used to perform joint power calculation on the basis of inclusion of 70 participants with varying levels of missing data. To determine the power, success rates were based on 1000 replicates of the study design.

Table 10 Covariance matrix used for Cmax and AUC(0-t) in power calculations

	AUC(0-t)	Cmax
AUC _{0-t}	0.814	0.685
Cmax	0.685	0.747

Table 11 Joint power calculation results (N=1000) across various scenarios of missing data

Scenario	Joint Power (CV% = 48% for both Cmax and AUC(0-t))	Joint Power (CV% = 68% and 62% for AUC(0-t) and Cmax respectively)
48 participants have complete data for Cmax and AUC(0-t) for all 4 periods and 22 Participants data is completely missing	90.3%	93.7%
48 participants have complete data for Cmax and AUC(0-t) for all 4 periods, 10 participants have 2 period data and 12 participants data is completely missing	93.4%	95.8%
48 participants have complete data for Cmax and AUC(0-t) for all 4	91.5%	94.9%

CONFIDENTIAL

221030

TMF-16298784	Protocol Version No. 1.0
periods, 6 participants have data for 2 periods and 16 remaining participants have no data at all	

Based on these results, and the aforementioned covariance matrix, at least 48 participants would be required to power a study to 90% to establish bioequivalence under the assumptions highlighted above. Based on experience, \sim 30% dropouts and/or withdrawals (due to unavoidable reasons like medical ground, adverse events, own accord, etc.) should be considered, requiring a target inclusion of 70 participants for this study. In-house data showed the variance of Cmax and AUC to be closer to 48%, implying that the above sample size calculation takes into account the worst-case scenario, and may in fact provide a power of >95%.

Sufficient number of volunteers will be asked to report on the day of check-in of period I in order to ensure that at least **70 participants** will be enrolled in the beginning of the study. Subsequent dropouts after dosing in period I will not be replaced.

Note: Additional participants if available, may be checked-in on the day of check in of period I to compensate for any dropout prior to dosing of period I. These participants will be dosed if there are dropouts prior to dosing in period I. If there are no dropouts, these participants will be checked-out without being dosed after completion of dosing in period I.

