4.2. Scientific rationale for study design

The manufacturing of albendazole tablets is being transferred from Cape Town, South Africa to Nashik, India. To ensure appropriate exposure after administration of the newly produced tablets from India, bioequivalence is required to be proven between the tablets from both locations. Therefore, this study evaluates the bioequivalence between the Sponsor's test study intervention (albendazole 400 mg tablets from Nashik, India) with respect to the reference study intervention (albendazole 400 mg tablets from Cape Town, South Africa) in healthy adult participants under fed condition.

Albendazole is a molecule with high intra-subject variability supported from literature² and in-house experience. Additionally, as per WHO product specific guidance (Notes on the Design of Bioequivalence Study: Albendazole; 29 March 2021), albendazole PK in the fed state is highly variable (up to 68% for Cmax and 62% for AUC). The WHO guideline for albendazole bioequivalence studies strongly recommends a replicate cross-over study design for albendazole bioequivalence studies, to estimate intra-subject PK variability more accurately which allows to widen the acceptance range for Cmax and AUC(0-t) ratios. Given the large variability in albendazole and albendazole sulfoxide PK, such potential larger differences in Cmax and AUC(0-t) between the proposed product and the comparator that might be accepted due to the widened acceptance range are expected to lack clinical relevance. In line with the WHO product specific guidance document, this study implements a fully replicate 4-period study design.

The PK sampling and washout period of 7 days are designed to ensure that PK parameters will be well-estimated and pre-dose concentrations are negligible in each subsequent period.

Depending on the CV% in Cmax and AUC(0-t), a joint power calculation showed that 48 evaluable participants were required to achieve a joint power of at least 90% for the two primary endpoints. Taking into account an expected dropout with fully missing data in up to 30% of participants, a total of 70 healthy adult participants will be enrolled. In case of only partially missing data in those 30%, the joint power of this study may be over 90% (Section 9.6).

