3.3 Sample Size

Based on the WHO guideline for albendazole, the maximum intra-subject variability observed for primary pharmacokinetic parameters Cmax and AUC(0-t) could be up to $\sim 68\%$ and 62% respectively. For this sample size calculation, a product difference of up to 10% (i.e. T/R ratio as 90.0-111.1%) has been assumed.

The sample size was determined using R software considering the following assumptions:

- a. T/R ratio = 90.0-111.1%
- b. Intra-Subject CV (%) $\sim 68\%$ (Cmax) and 62% (AUC(0-t)), or 48% (both)
- c. Significance Level = 5%

Correlation between Cmax and AUC(0-t) was calculated to be very high, based on an in-house albendazole study (GSK study O7921353). The exact Cmax and AUC(0-t) covariance matrix was calculated from this historical study as per below table and used to simulate realistic Cmax and AUC(0-t) values based on multivariate normal distributions. These values were then used to perform joint power calculation on the basis of inclusion of 70 participants with varying levels of missing data. To determine the power, success rates were based on 1000 replicates of the study design.

Table 1 Covariance matrix used for Cmax and AUC(0-t) in power calculations

	AUC(0-t)	Cmax
AUC _{0-t}	0.814	0.685
Cmax	0.685	0.747

Table 2 Joint power calculation results (N=1000) across various scenarios of missing data

Scenario	Joint Power (CV% = 48% for both Cmax and	Joint Power (CV% = 68% and 62% for AUC(0-t) and
	AUC(0-t)	Cmax respectively)
48 participants have complete data for Cmax and AUC(0-t) for all 4 periods and 22 Participants data is completely missing	90.3%	93.7%
48 participants have complete data for Cmax and AUC(0-t) for all 4 periods, 10 participants have 2 period data and 12 participants data is completely missing	93.4%	95.8%
48 participants have complete data for Cmax and AUC(0-t) for all 4 periods, 6 participants have data for 2 periods and 16 remaining participants have no data at all	91.5%	94.9%

Based on these results, and the aforementioned covariance matrix, at least 48 participants would be required to power a study to 90% to establish bioequivalence under the assumptions

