highlighted above. Based on experience, ~30% dropouts and/or withdrawals (due to unavoidable reasons like medical ground, adverse events, own accord, etc.) should be considered, requiring a target inclusion of 70 participants for this study. In-house data showed the variance of Cmax and AUC to be closer to 48%, implying that the above sample size calculation takes into account the worst-case scenario, and may in fact provide a power of > 95%.

Sufficient number of volunteers will be asked to report on the day of check-in of period I in order to ensure that at least **70 participants** will be enrolled in the beginning of the study. Subsequent dropouts after dosing in period I will not be replaced.

Note: Additional participants if available, may be checked-in on the day of check in of period I to compensate for any dropout prior to dosing of period I. These participants will be dosed if there are dropouts prior to dosing in period I. If there are no dropouts, these participants will be checked-out without being dosed after completion of dosing in period I.

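### Table 11 shows joint power rising from CV 48% to CV 68%/62%, but the plan's own decision rule makes it fall: about 93% to about 86% at T/R 0.90 with 48 completers and equal variances

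*Protocol*

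**What the plan says.** Protocol 9.6 assumes within-subject CVs of 68% (Cmax) and 62% (AUC(0-t)), or 48% for both, and "a product difference of up to 10% (i.e. T/R ratio as 90.0-111.1%) has been assumed". An in-house study supplies the dependence between endpoints: its "covariance matrix was calculated from this historical study (Table 10) and used to simulate realistic Cmax and AUC(0-t) values".

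Table 11, repeated as Table 2 in SAP 3.3, gives joint power from 1000 replicates:

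| Scenario | CV 48% | CV 68%/62% |
|---|---|---|
| 48 completers, 22 with no data | 90.3% | 93.7% |
| 48 completers, 10 with two periods, 12 with no data | 93.4% | 95.8% |
| 48 completers, 6 with two periods, 16 with no data | 91.5% | 94.9% |

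The second column is headed "Joint Power (CV% = 68% and 62% for AUC(0-t) and Cmax respectively", which reverses the assignment in assumption b.

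From this, 9.6 concludes that "at least 48 participants would be required to power a study to 90% to establish bioequivalence under the assumptions highlighted above", and Protocol 4.2 says "48 evaluable participants were required to achieve a joint power of at least 90% for the two primary endpoints". Because in-house variability was nearer 48%, 9.6 adds that the calculation "takes into account the worst-case scenario, and may in fact provide a power of >95" per cent. SAP 3.3 repeats this, "implying that the above sample size calculation takes into account the worst-case scenario".

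The decision rule is in Protocol 9.4.2.7 and SAP 6.3.2.8. The limits are exp(±0.760·sWR) when the reference CV exceeds 30%, capped at 69.84-143.19% from CV 50%. The GMR must lie within 80.00-125.00%, and Protocol 9.1 requires both endpoints to pass.

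**The concern.** If 68%/62% is the worst case, power there should be lower than at 48%. Table 11 shows the opposite in all three rows. The >95% remark about CV near 48% has no support in the 48% column, whose maximum is 93.4%; the only entry above 95% is in the high-CV column. The remark is not tied to a number of completers, so it is unsupported rather than impossible.

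The direction is also hard to square with the decision rule. Between CV 48% and CV 62-68% the limits barely widen, because the cap takes over at 50%, while the confidence interval keeps growing and the GMR constraint bites harder.

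At stake is the claim of at least 90% joint power with 48 evaluable participants at the highest CVs the plan says it covers. If the simulation did not apply the stated rule, the study was sized on a rule it will not use.

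**Working it through.** **Inputs.** Design TRTR/RTRT, 90% CI, T/R 0.90 (edge of the assumed range), CVs as above, 48 completers, rule as in 9.4.2.7. Correlation from Table 10: 0.685/√(0.814 × 0.747) = 0.878. Two inputs are assumptions because the documents do not state them: equal test and reference variances, and use of 0.878 as the within-subject correlation.

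**Hand check, one endpoint, 48 completers.** The log-scale variance is σ² = ln(1 + CV²). With two T and two R values per participant, the T−R contrast has variance σ²/2 + σ²/2 = σ², so SE = σ/√48. The ANOVA has 192 − 1 − 47 − 3 − 1 = 140 error df, so t = 1.656.

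| | CV 48% | CV 62% | CV 68% |
|---|---|---|---|
| σ² | 0.207 | 0.325 | 0.380 |
| σ | 0.455 | 0.570 | 0.617 |
| SE | 0.0657 | 0.0823 | 0.0890 |
| CI half-width, 1.656 × SE | 0.109 | 0.136 | 0.147 |
| Lower limit under the rule | 70.75% | 69.84% (cap) | 69.84% (cap) |
| Log distance from 0.90 to that limit | 0.241 | 0.254 | 0.254 |
| P(CI clears limit) ≈ Φ((distance − half-width)/SE) | 97.8% | 92.3% | 88.4% |
| P(GMR estimate > 0.80) = Φ(0.1178/SE), where 0.1178 = ln(0.90/0.80) | 96.3% | 92.4% | 90.7% |

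The limit can never be wider than the cap. An endpoint with CV 68% therefore passes at most about 88% of the time, and joint power cannot exceed that whatever the correlation. The stated 93.7% is not attainable at T/R 0.90 with equal variances.

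**Simulation of the full rule.** Fixed participant, period and formulation effects; sWR from the two reference periods; both endpoints must pass. The 48-completer row uses 100,000 trials (SE about 0.1 point).

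| Scenario | CV 48%: simulated (stated) | CV 68%/62%: simulated (stated) |
|---|---|---|
| 48 completers | 92.8% (90.3%) | 86.2% (93.7%) |
| plus 10 with two periods | 94.1% (93.4%) | about 89% (95.8%) |
| plus 6 with two periods | 93.6% (91.5%) | about 88% (94.9%) |

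The sponsor's Monte Carlo SE at 1000 replicates is √(0.903 × 0.097/1000) = 0.94 point for 90.3% and √(0.937 × 0.063/1000) = 0.77 point for 93.7%. The 48% figure is roughly reproduced, and a correlation of 0-0.5 brings it to 90-91%. The high-CV figure is 93.7 − 86.2 = 7.5 points too high, far beyond simulation error. Exchanging 68% and 62% between endpoints leaves joint power at about 86%.

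**Can another assumption give the printed table?** 48 completers, CV 48% then 68%/62%:

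| Variant | Joint power |
|---|---|
| T/R 0.89 | 90.0 / 83.3 |
| T/R 0.92 | 96.3 / 91.0 |
| T/R 0.935 | 97.8 / 93.8 |
| T/R 0.95 | 98.7 / 95.6 |
| T/R 1.00 | 99.7 / 97.8 |
| T/R 1.111 | 93.0 / 86.0 |
| Test/reference SD ratio 0.7 | 96.6 / 92.3 |
| SD ratio 0.9 | 94.2 / 88.8 |
| SD ratio 1.2 | 88.7 / 79.2 |
| Correlation 0 to 0.98 | 90.2-94.1 / 80.6-87.6 |
| Cap dropped | 92.6 / 88.0 |
| GMR constraint dropped | 93.9 / 86.1 |
| Both dropped | 94.3 / 97.3 |

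Power falls in every variant that keeps the plan's rule. It rises only when the cap and the GMR constraint are both left out. That makes their omission a candidate cause, not a proven one.

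**More completers.** With 56 (70 × 0.8), power is about 95% at CV 48% and about 90% at 68%/62%. With all 70 completing it is about 97% and about 93%.

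**Table 10.** Read as within-subject log variances, 0.814 and 0.747 mean CVs of √(e^0.814 − 1) = 112% for AUC(0-t) and √(e^0.747 − 1) = 105% for Cmax. The variances needed are 0.207, 0.325 and 0.380, so Table 10 as printed cannot be the within-subject matrix of either column. The scaling is not described.

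**The case against.** The strongest reply is that the two column headings were simply transposed. Swapped, the high-CV column reads 90.3/93.4/91.5%, which fits the worst-case wording, and the 48% column reads 93.7/95.8/94.9%, so >95% has one supporting entry. The heading already contains one transposition. At T/R 0.90 with equal variances, a swap leaves the high-CV figures about 3.5-4.5 points too high. The fit is better nearby: T/R 0.91 gives 94.7/88.9, 96.1/91.3 and 95.5/90.2 for the three rows (48%/high CV), and SD ratio 0.85 gives 94.7/89.6, 96.0/91.0 and 95.5/90.8. Five of the six swapped entries then lie within about 1.5 sponsor SEs; the second high-CV entry stays 2.1-2.4 points off. A label error is therefore a serious candidate, but it would still mean that the printed table is wrong.

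Secondly, the plan assumes a T/R range, not a point. Averaging over 0.90-1.11 gives 94.3/95.9/95.3% at high CV, close to the stated column. It also gives 97.9/98.4/98.4% at 48%, 5 to 8 points above what is stated, so power still falls. The documents do not settle which column is wrong, and the 86% and 14% figures are conditional.

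Thirdly, power does not fall with CV everywhere: with equal CVs it rises from 86.9% at 35% to about 92.7% near 48%, then falls to 84.4% at 68%. The claim here concerns 48% against 62-68%. The plan also never calls Table 10 within-subject, so the fair criticism there is the missing description. Finally, the final analysis uses observed data, so Table 11 cannot bias the trial result. These points limit the weight of the finding but do not remove the contradiction.

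**Conclusion.** The concern holds. Table 11 and SAP Table 2 contradict the text built on them, their high-CV heading reverses assumption b, and no assumption tested under the stated rule reproduces both columns as labelled.

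The size is conditional on T/R 0.90, equal variances and correlation 0.878. With 48 completers, the at-least-90% claim holds at CV 48% but not at 68%/62%, where the chance of failure is about 100 − 86.2 = 14% rather than the 100 − 93.7 = 6.3% implied. A T/R nearer 1 or a less variable test product raises the high-CV figure, but power still falls between 48% and 68%/62%. Neither the conclusion near CV 48% nor the enrolment of 70 is overturned.

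**What to change.** 1. Check whether the two column headings were transposed, and whether the simulation code applied the cap and the GMR constraint.
2. Re-run under the exact rule of Protocol 9.4.2.7 and SAP 6.3.2.8. State the T/R used, the test-variance assumption, whether Table 10 is a total or a within-subject matrix, and how it was scaled to 48% and to 68%/62%.
3. Replace Table 11 and SAP Table 2 with the sponsor's own re-run figures, and assign 68% and 62% to the endpoints as in assumption b.
4. Correct or delete the worst-case sentence in Protocol 9.6 and SAP 3.3, or tie it to a stated number of completers.
5. If the re-run confirms the fall, limit the claim of at least 90% power with 48 evaluable participants (Protocol 4.2 and 9.6, SAP 3.3) to CV near 48%.

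The cost is a short simulation and text edits. Enrolment, design and decision rule need no change.

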10.1. Appendix 1: Regulatory, ethical, and study oversight considerations

10.1.1. Regulatory and ethical considerations

- This study will be conducted in accordance with the protocol and with the following:
 - Consensus ethical principles derived from international guidelines including the Declaration of Helsinki (Brazil, October 2013) and CIOMS international ethical guidelines
 - o Applicable ICH GCP guidelines: [ICH E6(R2) 'Guideline for Good Clinical Practice' (2016)]
 - Applicable laws and regulations including current version of the [New Drugs & Clinical Trial Rules, 2019 of CDSCO, Ministry of health and family welfare, Government of India], [Ethical guidelines for biomedical research on human participants, ICMR ((2017)]
- Any significant change in the study procedure or study design will only be effected upon mutual agreement between the Sponsor and Lambda, and after obtaining a favorable opinion from the Ethics Committee.
- All such changes will be documented in the amended version of the protocol and a summary of changes with reference to the previous version will be generated. The protocol amendments, ICF and other relevant documents must be submitted to an IRB/IEC as soon as possible by the investigator and reviewed and approved by the IRB/IEC before the study is initiated.
- In cases where there is an immediate safety hazard to the participants, the amended protocol will be effective immediately and approval of the IEC/IRB will be obtained as soon as possible.
- Protocols and amendments to the protocol will require health authority approval prior to initiation except for changes necessary to eliminate an immediate hazard to study participants.
- This Protocol and the corresponding ICF used to obtain consent of study participants will be reviewed by the IEC/ IRB and the study will commence only after a written approval is obtained from the IEC/ IRB.
- The investigator will be responsible for the following, as applicable:
 - Providing written summaries of the status of the study to the IRB/IEC annually or more frequently in accordance with the requirements, policies, and procedures established by the IRB/IEC
 - Notifying the IRB/IEC of SAEs or other significant safety findings as required by IRB/IEC procedures
 - Providing oversight of the conduct of the study at the site and adherence to requirements of 21 CFR, ICH guidelines, the IRB/IEC, European regulation 536/2014 for clinical studies (if applicable), and all other applicable local regulations

10.1.2. Financial disclosure

Not Applicable.

10.1.3. Informed consent process

- The investigator or the investigator's representative will explain the nature of the study, including the risks and benefits and information regarding the study intervention to the participants/ LAR(s) and answer all questions regarding the study at the time of ICF presentation. This will be done through an oral presentation regarding the purpose, procedures to be carried out, potential hazards and rights of the participants, in their local language. Participants will be encouraged to ask questions and clarify their doubts regarding any aspect of the study.
- Potential participants/ LAR(s) must be informed that their participation is voluntary. They or their LARs will be required to physically sign/ put a thumb impression on a statement of informed consent that meets the requirements of 21 CFR 50, local regulations, ICH guidelines, HIPAA requirements, privacy and data protection requirements, where applicable, and the IRB/IEC or study center.
- Participants will be required to sign / put a thumb impression on the informed consent form summarizing the discussion prior to check-in for the study. Signature of the LAR/Impartial witness (if applicable) will be taken on the informed consent form in case the Participant is not able to sign on the informed consent form. Participants who fail to understand the informed consent procedure and/or are unable to communicate with the study personnel will not be enrolled.
- The physical informed consent will be obtained before the participant gets enrolled in the study and the date of the physical consent was obtained. The authorized person obtaining the informed consent must also sign the ICF.
- Participants must be reconsented to the most current version of the ICF(s) during their participation in the study.
- The Participants will give their consent for participation in the trial by signing /putting a thumb impression on ICF, which will also be signed by the LAR/Impartial witness (if applicable) and Lambda's person conducting the ICF presentation, principal investigator or designate.
- A photocopy of ICF with the signature or thumb impression must be provided to the participant or their LAR, while the original will be retained at Lambda Therapeutic Research Ltd.

